9.10 OTHER ASPECTS

9.10.1 Data quality assurance

A quality assurance audit/inspection of this study may be conducted by the sponsor or sponsor's designees. The quality assurance auditor will have access to all study-related files.

9.10.2 Study records

Not applicable. (This study will not use Case Report Forms.)

9.10.3 Completion of study

Not applicable.

9.10.4 Protocol deviations

Deviations from the research protocol that may occur in this study include deviations from the procedures for handling databases and methods of analysis and reporting. Any deviations should be reported to the principal investigator by the co-investigator or contract research organization.

9.10.5 Compensation available to the patient in the event of study related injury

Not applicable.

10. PROTECTION OF HUMAN SUBJECTS

The MDV data used in this study is existing information and does not involve the acquisition of new information. In addition, it is anonymized processed information and cannot identify individuals. Therefore, the protection of subjects does not apply to this study.

11. MANAGEMENT AND REPORTING OF ADVERSE EVENTS/ADVERSE REACTIONS

Not applicable based on secondary use of data without any potential that any employee of BI or agent working on behalf of BI will access individually identifiable patient data.

12. PLANS FOR DISSEMINATING AND COMMUNICATING STUDY RESULTS

The results of this research will be presented at conferences and published in peer-reviewed journals.

ANNEX 1. LIST OF STAND-ALONE DOCUMENTS

Number	Document Reference Number	Date	Title
1	Annex 1	20 February 2023	List of stand-alone documents
2	Annex 2	20 February 2023	INTERSTITIAL LUNG DISEASE PROGRESSION PROXIES
3	Annex 3	20 February 2023	CODE FOR TREATMENT, MANAGEMENT & CLNICAL EXAMINATION
4	Annex 4	20 February 2023	CODE FOR COMORBIDITY AND MEDICAL HISTORY
5	Annex 5	20 February 2023	ALGORITHMS FOR DEFINING UDERLYING DISEASES
6	Annex 6	20 February 2023	INFORMATION OF THE CODE TO DEFINE FIBROSING ILD AND UNDERLYING DISEASES
7	Annex 7	20 February 2023	REVIEWERS AND APPROVAL SIGNATURES

ANNEX 2. INTERSTITIAL LUNG DISEASE PROGRESSION PROXIES

Proxy	billing code / generic names / EphMRA ATC code
≥ 3 pulmonary function tests on different dates of service within 365 days The date of the 3 rd pulmonary function test will be the date of progression	160062610 160062710 160062810
≥ 3 HRCT/CT on different dates of service within 365 days The date of the 3 rd HRCT/CT will be the date of progression	170022290 170011710 170011810 170028610 170033410 170034910 170040210 170040410 170040610 170040810 170041010
≥ 1 claim for oxygen therapy (HOT) during follow-up period	114003710
≥ 1 respiratory hospitalization during follow-up period	A221 A379 A370 B250 B440 J00 J01.x J02.x J03.x J04.x J05.x J06.x J110 J12.x J13 J14 J15.x J160 J18.x J20x J21.x J22 J40 J41.x J42 J43.x J44.x J45.x J84.x J96.x Segment of disease based on DPC is “01: Disease name which input the most medical resources”, “11: Main disease name”, or “21: Disease name behind hospitalization”
≥ 1 claim for palliative care during follow-up period	Oxygen inhalation: 140005610 Opioid use:

	N02A0 [Excluding methadone, buprenorphine, naloxonecombinations (Suboxone)] * *transdermal patch, sublingual agent, Transmucosal agent, suppository are excluded
≥ 1 lung transplant during follow-up period	K514-4 K514-6
≥ 1 new* claim for immunosuppressive drugs during follow-up period with at least two out of the three test codes** within 3 months before new claims for immunosuppressive drugs Rituximab Tacrolimus Mycophenolate Cyclosporine Cyclophosphamide Azathioprine Tocilizumab	Rituximab/ L01G1 Tacrolimus/ L04X0 Mycophenolate/ L04X0 Cyclosporine or (Ciclosporin, Cyclosporin) / L04X0 Cyclophosphamide/ L01A0 Azathioprine/ L04X0 Tocilizumab/ M01C0 & L04C0 (Generic names/ MphMRA ATC codes which each drug is under)
≥ 1 new* claim for oral corticosteroid with a prednisone-equivalent dose of >20 mg during follow-up period and with at least two out of the three test codes* within 3 months before new claims for oral corticosteroid *: Not received in the 12 months prior to the index date **: ① Pulmonary function tests, ② HRCT/CT, ③ KL-6 or SP-D	H02A2 excluding Florinef
≥ 1 claim for Nintedanib* during follow-up period *: Patients meeting this criterion will be counted only if patients with fibrosing ILDs meet this criterion on or after 29-May-2020, because nintedanib was approved for PF-ILD on 29-May-2020. Even if patients with fibrosing ILDs meet this criterion on or before 28-May-2020, they will not be counted.	Nintedanib/ L01H9 & R07D0 (Generic name/ MphMRA ATC codes which nintedanib is under)

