9.2.2 Study population

9.2.2.1 Eligibility criteria

Patients who meet all of the inclusion criteria and do not meet any of the exclusion criteria will be included in the study population.

Inclusion Criteria:

- 1) Patients diagnosed with at least two fibrosing ILD codes^{*1} on different dates in the patient identification period from 01-Jan-2013 to 6 months before 28-May-2020
- 2) Patients aged 18 years and older on the index date
- 3) Patients for whom data for the 12 months prior to the index date can be extracted as baseline data

*1 International Statistical Classification of Diseases and Related Health Problems (ICD-10) code or disease code: J84.1, J84.9, 8844510, 8848382, 8844341, 8848278, 8836513, 8848267, 8848302, 8839362, 8848283, 8837013, 8834158, 8848245, 8840951, 8847737

Exclusion Criteria:

- 1) Patients grouped into the underlying disease of IPF^{*1}
- 2) Patients who have met PF-ILD progression criteria during the baseline period

*1 Please refer to the ANNEX 5 for algorithm to define underlying diseases

Note: only diagnosis records without 'suspect flag' are to be considered for evaluating diagnosis related in/excl criteria"

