9.7.3 Subgroup analysis

The three subgroup analyses by underlying diseases defined by disease codes on the index date and 12-months lookback period as described in Annex 5 will be performed for patient background characteristics and treatment, primary outcome, and secondary outcomes.

<Subgroup Patterns>

Underlying Autoimmune Disease (Subgroup1): Autoimmune ILD, Non-autoimmune ILD, Multiple, Unknown

ILD Category (Subgroup 2): Hypersensitive pneumonitis, Exposure-related ILD, iNSIP, Unclassifiable IIP, Sarcoidosis, RA-ILD, SSc-ILD, MCTD-ILD, Other autoimmune ILD, Other ILD, Multiple, Unknown

Pre-Specified ILD Clinical Diagnosis (Subgroup 3): Hypersensitive pneumonitis, Exposure-related ILD, iNSIP, Unclassifiable IIP, Sarcoidosis, RA-ILD, SSc-ILD, MCTD-ILD, SLE-ILD, PM/DM-ILD, Sjogren ILD, Other autoimmune ILD, Other ILD, Multiple, Unknown

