ANNEX 6. INFORMATION OF THE CODE TO DEFINE FIBROSING ILD AND UNDERLYING DISEASES

Disease	ICD-10 Code	billing code	Underlying Autoimmune Disease	ILD Category	Pre-Specified ILD Clinical Diagnosis
respiratory disorder in dermatosclerosis	M348	8844510	autoimmune	SSc-ILD	SSc-ILD
rheumatoid arthritis interstitial pneumonia	M0510	8847737	autoimmune	RA-ILD	RA-ILD
respiratory disorder complicated by granulomatosis with polyangiitis	M313	8848382	autoimmune	Other autoimmune ILDs	Other autoimmune ILDs
systemic lupus erythematosus interstitial pneumonia	M321	8848278	autoimmune	SLE-ILD	other autoimmune ILDs
respiratory disorder in systemic lupus erythematosus	M321	8836513	autoimmune	SLE-ILD	other autoimmune ILDs
interstitial pneumonia in juvenile dermatomyositis	M330	8848267	autoimmune	PM/DM ILD	other autoimmune ILDs
interstitial pneumonia in dermatomyositis	M331	8848302	autoimmune	PM/DM ILD	other autoimmune ILDs
respiratory disorder in dermatomyositis	M331	8839362	autoimmune	PM/DM ILD	other autoimmune ILDs
interstitial pneumonia in polymyositis	M332	8848283	autoimmune	PM/DM ILD	other autoimmune ILDs
respiratory disorder in polymyositis	M332	8837013	autoimmune	PM/DM ILD	other autoimmune ILDs
respiratory disorder in Sjogren's syndrome	M350	8834158	autoimmune	Sjogren ILD	other autoimmune ILDs

Disease	ICD-10 Code	billing code	Underlying Disease	Autoimmune	ILD Category	Pre-Specified Diagnosis	ILD	Clinical
postinflammatory pulmonary fibrosis	J841	8845640	Non-autoimmune		Unclassifiable	Unclassifiable		
usual interstitial pneumonia	J841	5168008	Non-autoimmune		Unclassifiable	Unclassifiable		
idiopathic interstitial pneumonia	J841	5168009	Non-autoimmune		Unclassifiable	Unclassifiable		
diffuse interstitial pneumonia	J841	5150001	Non-autoimmune		Unclassifiable	Unclassifiable		
diffuse alveolar damage	J841	8845731	Non-autoimmune		Unclassifiable	Unclassifiable		
idiopathic pulmonary fibrosis	J841	5163005	IPF		IPF	IPF		
pulmonary fibrosis	J841	5150011	IPF		IPF	IPF		
combined pulmonary fibrosis and emphysema	J841	8849927	IPF		IPF	IPF		
Idiopathic nonspecific interstitial pneumonia	J841	8850547	Non-autoimmune		iNSIP	iNSIP		

nonspecific interstitial pneumonia	J841	8845727	Non-autoimmune	iNSIP	iNSIP
acute interstitial pneumonia	J84.1	1363003	Non-autoimmune	Other IIPs	Other IIPs
respiratory bronchiolitis-associated interstitial lung disease	J841	8845663	Non-autoimmune	Other IIPs	Other IIPs
cryptogenic organizing pneumonia	J841	8845714	Non-autoimmune	Other IIPs	Other IIPs

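### The Annex 2 respiratory-hospitalization proxy lists none of the 14 autoimmune-ILD disease codes that qualify patients for the cohort, so ascertainment of progression depends on how an ILD admission is coded

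*Combined protocol and SAP*

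**What the plan says.** **Entry.** Inclusion criterion 1 (section 9.2.2.1) requires two fibrosing-ILD codes on different dates. The codes are "J84.1, J84.9, 8844510, 8848382, 8844341, 8848278, 8836513, 8848267, 8848302, 8839362, 8848283, 8837013, 8834158, 8848245, 8840951, 8847737". Annex 6 gives the meaning of each seven-digit code, for example "respiratory disorder in dermatosclerosis M348 8844510" for SSc-ILD and, for 8847737, "rheumatoid arthritis interstitial pneumonia".

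**Event.** Table 1 (section 9.3.1.1) makes a single respiratory hospitalization in follow-up sufficient for progression to PF-ILD. The event date is the date on which a criterion is met. Annex 2 supplies the codes: "A221 A379 A370 B250 B440 J00 J01.x J02.x J03.x J04.x J05.x J06.x J110 J12.x J13 J14 J15.x J160 J18.x J20x J21.x J22", continuing with "J40 J41.x J42 J43.x J44.x J45.x J84.x J96.x Segment of disease based on DPC is". The DPC segments searched are "01: Disease name which input the most medical resources”, “11: Main disease name”, or “21: Disease name behind hospitalization".

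**Baseline exclusion.** Exclusion criterion 2 removes "Patients who have met PF-ILD progression criteria during the baseline period". No separate code list is given for it, so the Annex 2 list applies.

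**Reporting.** Section 9.7.3 plans "The three subgroup analyses by underlying diseases defined by disease codes on the index date" and the 12-month lookback. They cover the primary outcome, both for autoimmune against non-autoimmune ILD and by individual disease.

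**The concern.** The protocol treats a diagnosis of rheumatoid arthritis interstitial pneumonia as fibrosing ILD when it builds the cohort, but does not treat an admission under that same name as respiratory. An admission under J84.1 or J84.9 does count. So does one under J41 to J44, the range that Annex 4 uses for COPD. No reason is given for the difference.

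Three things are at stake.

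- The proxy is a single-claim route into the primary outcome, so one unrecognised admission can mean one lost event.
- If another proxy catches the patient later, the event is still dated too late. That can move the 6- and 12-month estimates even where the 24-month estimate changes little.
- The same list works at baseline. A patient admitted for ILD in the baseline year is excluded if the admission was coded J84, but may stay in the risk set if it was coded with an autoimmune-ILD disease name.

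The missing codes are also the ones from which the autoimmune subgroups are partly built. Estimates that will be read side by side are therefore not all produced by the same measurement rule.

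**Working it through.** The plan states no figure on this point, so the check compares code sets.

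**Step 1: entry codes (section 9.2.2.1).** 2 ICD-10 categories (J84.1, J84.9) + 14 disease codes = 16 entries.

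**Step 2: ICD-10 codes of the 14 (Annex 6).**

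| ICD-10 in Annex 6 | Disease codes | Number |
|---|---|---|
| M05.10 | 8847737, 8840951 | 2 |
| M31.3 | 8848382 | 1 |
| M32.1 | 8848278, 8836513, 8844341 | 3 |
| M33.0 | 8848267 | 1 |
| M33.1 | 8848302, 8839362 | 2 |
| M33.2 | 8848283, 8837013 | 2 |
| M34.8 | 8844510 | 1 |
| M35.0 | 8834158 | 1 |
| M35.1 | 8848245 | 1 |

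Sum: 2 + 1 + 3 + 1 + 2 + 2 + 1 + 1 + 1 = 14, over nine ICD-10 codes, all in chapter M.

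**Step 3: hospitalization list (Annex 2).** 22 + 8 = 30 entries. All begin with A, B or J. There is no M code and no seven-digit disease code.

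**Step 4: match.** Each entry code was compared with the list, directly and by ICD-10 prefix. J84.1 and J84.9: 2 of 2 matched, through J84.x. Autoimmune-ILD disease codes: 0 of 14 matched.

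**Step 5: link to the subgroups (Annex 5).** Twelve of the 14 are the Step 1 codes, which assign a patient to autoimmune ILD unless the rule for multiple diseases applies. The other two (8840951, 8848245) lead to autoimmune ILD in Step 2 or 3, again unless that rule applies.

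**Step 6: direction.** Two mechanisms act, and they can oppose each other. Let p be the 24-month probability of an event through the other proxies, a the probability of an ILD admission, and m the share of admissions carrying only an unlisted code. Assume independence.

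- With full ascertainment, incidence is 1 − (1 − p)(1 − a). With the gap it is 1 − (1 − p)(1 − a(1 − m)). The loss is (1 − p) × a × m.
- If a share w of the group consists of retained patients with a baseline admission, and their observed incidence exceeds that of the rest by d, the estimate rises by w × d.
- The two cancel when w × d = (1 − p) × a × m.

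Purely for illustration, take p = 30% and a = 10%. Full ascertainment gives 1 − 0.70 × 0.90 = 37.0%. The first mechanism alone gives:

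- m = 25%: 1 − 0.70 × 0.925 = 35.25%, a loss of 1.75 points
- m = 50%: 1 − 0.70 × 0.95 = 33.5%, a loss of 3.5 points
- m = 75%: 1 − 0.70 × 0.975 = 31.75%, a loss of 5.25 points

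These losses are offset in full when w × d reaches 1.75, 3.5 or 5.25 points, and are reversed beyond that. The documents give none of p, a, m, w or d.

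**The case against.** Several stronger readings are tempting, and the documents do not support them.

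- **An autoimmune-ILD admission never counts.** Annex 2 accepts a listed code in any one of three segments, so an admission that also carries J84.x, J96.x or J18.x there does count. The patient may also qualify through oxygen inhalation, home oxygen, a third CT or pulmonary function test within 365 days, or a new immunosuppressant or corticosteroid claim with the required tests. The loss is partial.
- **The autoimmune subgroups are the M-coded patients.** Annex 5 Step 2 places patients with J84.1 or J84.9 on the index date and an earlier autoimmune code into RA-ILD, SSc-ILD, SLE-ILD, PM/DM-ILD and Sjogren ILD. MCTD-ILD can be reached only that way. A patient's index code also does not fix the code on a later admission.
- **Non-autoimmune subgroups are measured completely.** J67.x, the exposure-related codes and D86.x are absent from the list too. Hypersensitivity pneumonitis, exposure-related ILD and sarcoidosis can lose admissions coded only that way.
- **14 of 16 entry codes measures the loss.** That ratio mixes ICD-10 categories with single disease codes. Annex 6 lists 17 disease codes under J84.1 and J84.9, of which 3 are IPF. Like for like, the omission is 14 of 14 + 17 = 31, or 14 of 14 + 14 = 28 without IPF. None of these is a share of patients or admissions.
- **Incidence in autoimmune ILD is understated by roughly 2 to 5 points.** The illustration above rests on assumed inputs and on an independence that is doubtful, because admission, oxygen, imaging and steroids tend to occur together. It also leaves out the baseline mechanism.

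The plan's defenders can add that section 9.9 discloses an unvalidated algorithm and possible bias, and that the subgroup results are descriptive with no formal comparison. Both are true, but neither closes the gap. Section 9.9 does not mention ascertainment that differs by coding. The two firm sensitivity analyses in section 9.7.4 change the data cut-off and the index date, not this list. The modified-criteria analysis is optional. It would be guided by proxy patterns among patients who already met a criterion, and patients missed altogether are not in that group.

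**Conclusion.** The inconsistency is established from the text: 0 of the 14 autoimmune-ILD entry codes can satisfy the respiratory-hospitalization proxy, against 2 of 2 for J84.1 and J84.9. An admission whose segments 01, 11 and 21 carry only such a code does not meet this proxy in follow-up and does not trigger exclusion 2 through it. Ascertainment of the primary outcome therefore differs between ILD admissions coded J84 and those coded with autoimmune-ILD disease names. This bears on the overall estimate and on the planned autoimmune, non-autoimmune and disease-specific estimates.

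Its size and net sign are unknown, because the documents give no admission counts and no coding frequencies. The conclusion rests on two readings: that Annex 2 is the complete list for this proxy, since Table 1 gives nothing wider, and that exclusion 2 uses it unchanged. The point should be settled before the subgroup incidences are interpreted.

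**What to change.** In Annex 2, add the 14 disease codes of section 9.2.2.1 to the respiratory-hospitalization list, and state that exclusion criterion 2 uses the same list. Add them by disease code, not by ICD-10 category. Annex 6 shows why: M35.0 also covers Sjogren's syndrome without lung involvement and its myopathy, and M35.1 covers overlap syndrome and mixed connective tissue disease. If the DPC segments hold only ICD-10 codes, the protocol should say so and state the rule used instead. If the sponsor prefers to keep the present list, it should give the reason and commit to a sensitivity analysis with the codes added.

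This raises the entry codes recognised by the proxy from 2 to 16 of the 16 entries. The cost is a code-list edit, a rerun and slightly more baseline exclusions in the autoimmune subgroups. The amendment table already records four changes to codes or drug definitions in Annexes 2 and 3.

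As a secondary sensitivity analysis, extend the list to the underlying-disease lung codes that are not entry codes: J67.x, the exposure-related J codes and the lung sarcoidosis codes. Treat the three groups alike. Adding only some of them would leave another subgroup unequal.

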ANNEX 3. CODE FOR TREATMENT, MANAGEMENT & CLNICAL EXAMINATION

Drug name / Treatment	Generic names/ Codes
Rituximab	Rituximab/ L01G1
Tacrolimus	Tacrolimus/ L04X0
Mycophenolate	Mycophenolate/ L04X0
Cyclosporine	Cyclosporine or (Ciclosporin, Cyclosporin)/ L04X0
Cyclophosphamide	Cyclophosphamide/ L01A0
Azathioprine	Azathioprine/ L04X0
Oral Corticosteroid	H02A2 excluding Florinef
Tocilizumab	Tocilizumab/ M01C0 & L04C0
Nintedanib	Nintedanib/ L01H9 & R07D0
Oxygen therapy (HOT)	114003710
Lung transplant	K514-4 K514-6
Palliative care	Oxygen inhalation: 140005610 Opioid use: N02A0 [Excluding methadone, buprenorphine, naloxonecombinations (Suboxone)] * *transdermal patch, sublingual agent, Transmucosal agent, suppository are excluded
PFT	160062610 160062710 160062810
HRCT/CT	170022290 170011710 170011810 170028610 170033410 170034910 170040210 170040410 170040610 170040810 170041010
KL-6	160168550
SP-D	160168450

ANNEX 4. CODE FOR COMORBIDITY AND MEDICAL HISTORY

Comorbidity / Medical history	Codes
Coronary heart disease	I20-25
Gastro-esophageal reflux disease	K21
Obstructive sleep apnoea syndrome	G473
COPD	J41-44
Lung cancer	C34
Pulmonary hypertension	I27

ANNEX 5. ALGORITHMS FOR DEFINING UNDERLYING DISEASES

The following three subgroups will be defined to assess the distribution of underlying diseases and to perform subgroup analysis by underlying diseases.

Subgroup1: Autoimmune ILD, Non-autoimmune ILD, Multiple, Unknown, IPF[#]

Subgroup2: Hypersensitive pneumonitis, Exposure-related ILD, iNSIP, Unclassifiable IIP, Sarcoidosis, RA-ILD, SSc-ILD, MCTD-ILD, Other autoimmune ILD, Other ILD, Multiple, Unknown, IPF[#]

Subgroup3: Hypersensitive pneumonitis, Exposure-related ILD, iNSIP, Unclassifiable IIP, Sarcoidosis, RA-ILD, SSc-ILD, MCTD-ILD, SLE-ILD, PM/DM-ILD, Sjogren ILD, Other autoimmune ILD, Other ILD, Multiple, Unknown, IPF[#]

#Note: Patients grouped into IPF are excluded from study population according to the exclusion criteria.

The patients will be grouped according to the following three steps.

Step 1: Patients will be grouped based on the fibrosing-ILD code on the index date

If two or more different ⁽¹⁾ disease codes specified in this step 1 exist on index date, then subgroup1=subgrou2=subgrou3=Multiple

else if disease code on index date=8844510, then Subrgou1=Autoimmune ILD, subgroup2=SSc-ILD, subgroup3=SSc-ILD

else if disease code on index date=8847737, then subgroup1=Autoimmune ILD, subgroup2=RA-ILD, subgorup3=RA-ILD

else if disease code on index date=8848382, then subrgou1=Autoimmune ILD, subgroup2=Other autoimmune ILD, subgroup3=Other autoimmune ILD

else if disease code on index date=in(8848278, 8836513, 8844341), then subgroup1=Autoimmune ILD, subgroup2=Other autoimmune ILD. Subgroup3=SLE-ILD

else if disease code on index date=in(8848267, 8848302, 8839362, 8848283, 8837013), then subgroup1=Autoimmune ILD, subgroup2=Other autoimmune ILD, subgroup3=PM/DM ILD

else if disease code on index date=8834158, then subgroup1=Autoimmune ILD, subgroup2=Other autoimmune ILD, subgroup3=Sjogren ILD

(1)Note: The disease codes in the same conditional statement are NOT considered different. For example, disease codes of 8848278 and 8836513 are in the same conditional statement and these are not considered different disease codes. On the other hand, disease codes of 8848278 and 8848267 are in the different conditional statement and these are considered different disease codes.

Step 2: Patients not grouped in the step 1 will be grouped based on the earliest underlying disease code in the lookback period and fibrosing-ILD code on the index date

else if two or more different ⁽²⁾ earliest underlying disease codes specified in this step 2 exist AND disease code on index date=in(J84.1, J84.9), then subgroup1=subgou2=subgrou3=Multiple

else if earliest underlying disease code=in(D86.0, D86.1, D86.3, D86.8, D86.9) AND disease code on index date=in(J84.1, J84.9), then subgroup1=Non-autoimmune ILD, subgroup2=Sarcoidosis, subgroup3=Sarcoidosis

else if earliest underlying disease code=in(J67.0, J67.1, J67.2, J67.3, J67.4, J67.5, J67.6, J67.7, J67.8, J67.9) AND disease code on index date=in(J84.1, J84.9), then subgroup1=Non-autoimmune ILD, subgroup2=Hypersensitive pneumonitis, subgroup3=Hypersensitive pneumonitis

else if earliest underlying disease code=J84.0 AND disease code on index date=in(J84.1, J84.9), then subgroup1=Non-autoimmune ILD, subgroup2=Other ILD, subgroup3=Other ILD

else if earliest underlying disease code=in(J60, J61, J62.8, J63.0, J63.1, J63.2, J63.3, J63.4, J63.5, J64, J65, J66.0, J66.1, J68.0, J68.4, J70.1, J70.3, J70.4, J70.8) AND disease code on index date=in(J84.1, J84.9), then subgroup1=Non-autoimmune ILD, subgroup2=Exposure-related ILD, subgroup3=Exposure-related ILD

Note: Disease codes of 8840951 and 8848245 are added to the coitional statement.

else if earliest underlying disease code=in(M05.0, M05.1, M05.2, M05.3, M05.8, M05.9, M06.0, M06.2, M06.3, M06.4, M06.8, M06.9) AND disease code on index date=in(J84.1, J84.9, 8840951, 8848245), **then** subgroup1=Autoimmune ILD, subgroup2=RA-ILD, subgroup3=RA-ILD

else if earliest underlying disease code=in(M32.1, M32.9) AND disease code on index date=in(J84.1, J84.9, 8840951, 8848245), **then** subgroup1=Autoimmune ILD, subgroup2=Other autoimmune ILD, subgroup3=SLE-ILD

else if earliest underlying disease code=in(M33.0, M33.1, M33.2, M33.9) AND disease code on index date=in(J84.1, J84.9, 8840951, 8848245), **then** subgroup1=Autoimmune ILD, subgroup2=Other autoimmune ILD, subgroup3= PM/DM ILD

else if earliest underlying disease code=in(M34.0, M34.1, M34.8, M34.9) AND disease code on index date=in(J84.1, J84.9, 8840951, 8848245), **then** subgroup1=Autoimmune ILD, subgroup2=SSc-ILD, subgroup3=SSc-ILD

else if earliest underlying disease code=M35.0 AND disease code on index date=in(J84.1, J84.9, 8840951, 8848245), **then** subgroup1=Autoimmune ILD, subgroup2=Other autoimmune ILD, subgroup3=Sjogren ILD

else if earliest underlying disease code=7109008 AND disease code on index date=in(J84.1, J84.9, 8840951, 8848245), **then** subgroup1=Autoimmune ILD, subgroup2=MCTD-ILD, subgroup3=MCTD-ILD

else if earliest underlying disease code=in(8841317, 8850417, 8848245, M35.2, M35.3, M35.4, M35.5, M35.6, M35.7, M35.8, M35.9, M30.0, M30.1, M30.2, M30.3, M30.8, M31.0, M31.1, M31.2, M31.3, M31.4, M31.6, M31.7, M31.8, M31.9) AND disease code on index date=in(J84.1, J84.9, 8840951, 8848245), **then** subgroup1= Autoimmune ILD, subgroup2=Other autoimmune ILD, subgroup3=Other autoimmune ILD

(2)Note: The earliest underlying disease codes in the same conditional statement are NOT considered different. For example, earliest underlying disease codes of D86.0 and D86.1 are in the same conditional statement and these are not considered different earliest underlying disease codes. On the other hand, earliest underlying disease codes of D86.0 and J67.0 are in the different conditional statement and these are considered different earliest underlying disease codes.

Step 3: Patients not grouped in the step 1 and 2 will be grouped based on the fibrosing-ILD code on the index date

else if disease code on index date=in(5163005, 5150011, 8849927) AND no other fibrosing-ILD code on the index date, **then** subgroup1=subgroup2=subgroup3=IPF. These patients will be excluded from study population.

else if two or more different ⁽³⁾ disease codes including disease code of IPF specified in this step 3 exist on index date, **then** subgroup1=subgorup2=subgrou3=Multiple

else if disease code on index date=in(8850547, 8845727), **then** subgroup1=Non-autoimmune ILD, subgroup2=iNSIP, subgroup3=iNSIP

else if disease code on index date=in(5168008, 5168009, 5150001, 8845731, 8845640, J84.9), **then** subgroup1=Non-autoimmune ILD, subgroup2=Unclassifiable IIP, subgroup3=Unclassifiable IIP

else if disease code on index date=in(1363003, 8845663, 8845714, 8845719, 5168010), **then** subgroup1=Non-autoimmune ILD, subgroup2=Other ILD, subgroup3=Other ILD

else if disease code on index date=in(8840951, 8848245), **then** subgroup1=Autoimmune ILD, subgroup2=Other autoimmune ILD, subgroup3=Other autoimmune ILD

else subgroup1=subgroup2=subgroup3=Unknown

(3)Note: The disease codes in the same conditional statement are NOT considered different. For example, disease codes of 8850547 and 88457271 are in the same conditional statement and these are not considered different disease codes. On the other hand, disease codes of 8850547 and 5168008 are in the different conditional statement and these are considered different disease codes.

END

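### Annex 5 sets all three subgroup variables to Multiple on one test per step, so some patients whose codes agree on the autoimmune class, or on the ILD category, lose that label in the subgroup analyses.

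*Combined protocol and SAP*

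**What the plan says.** Section 9.7.3 plans three subgroup analyses by underlying disease, covering background characteristics and treatment, the primary outcome and the secondary outcomes. The coarsest is "Underlying Autoimmune Disease (Subgroup1): Autoimmune ILD, Non-autoimmune ILD, Multiple, Unknown". Subgroup 2 has 12 levels and Subgroup 3 has 15. The section does not rank them. Section 9.7.4 repeats all analyses in the sensitivity runs.

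Annex 5 assigns the levels in three steps, each with its own rule for Multiple:

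- Step 1 uses ILD-specific autoimmune codes on the index date. The rule applies if two or more different "disease codes specified in this step 1 exist on index date, then subgroup1=subgrou2=subgrou3=Multiple".
- Step 2 uses the earliest underlying disease code in the lookback period together with the index code. The rule applies if two or more different "earliest underlying disease codes specified in this step 2 exist AND disease code on index date=in(J84.1, J84.9), then subgroup1=subgou2=subgrou3=Multiple".
- Step 3 returns to the index-date codes. The rule applies if two or more different "disease codes including disease code of IPF specified in this step 3 exist on index date", and again all three variables become Multiple.

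The notes to each step define different codes as codes in different conditional statements. Note (1) gives an example: "disease codes of 8848278 and 8848267 are in the different conditional statement and these are considered different disease codes".

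**The concern.** The test works at the level of the conditional statements, which is essentially the granularity of Subgroup 3, but its result is also written to the two coarser variables. Note (1)'s own example shows the effect. The first code belongs to the statement "in(8848278, 8836513, 8844341), then subgroup1=Autoimmune ILD, subgroup2=Other autoimmune ILD. Subgroup3=SLE-ILD" and the second to "in(8848267, 8848302, 8839362, 8848283, 8837013), then subgroup1=Autoimmune ILD, subgroup2=Other autoimmune ILD, subgroup3=PM/DM ILD". The two agree at Subgroup 1 and at Subgroup 2 and differ only at Subgroup 3, yet a patient with both is Multiple throughout.

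Section 7 gives estimation of progression by underlying disease as part of the study's purpose. Under the rule, the Autoimmune ILD and Non-autoimmune ILD Kaplan-Meier estimates omit some patients whose class is not in doubt, while keeping the class names. Subgroup 1 Multiple becomes a pool of autoimmune-only, non-autoimmune-only and truly mixed patients, which is hard to interpret.

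**Working it through.** **Inputs.** The conditional statements of Annex 5 and the labels each one assigns. The plan gives no figure to reproduce.

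- Step 1 has 6 statements, all Autoimmune ILD at Subgroup 1. At Subgroup 2 they are SSc-ILD, RA-ILD and four that map to Other autoimmune ILD (granulomatosis with polyangiitis, SLE, PM/DM, Sjogren).
- Step 2 has 11 statements. Four are non-autoimmune (sarcoidosis, hypersensitivity pneumonitis, J84.0, exposure-related). Seven are autoimmune (RA, SLE, PM/DM, SSc, Sjogren, MCTD, other), and four of these seven map to Other autoimmune ILD.
- Step 3 has 5 statements: IPF, three non-autoimmune (iNSIP, unclassifiable, other ILD) and one autoimmune, "else if disease code on index date=in(8840951, 8848245".

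**Pairs that become Multiple as written**, n(n−1)/2: Step 1, 6×5/2 = 15; Step 2, 11×10/2 = 55; Step 3, 5×4/2 = 10.

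**Pairs that agree at Subgroup 1.**

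- Step 1: all 15, both autoimmune.
- Step 2: 7×6/2 = 21 both autoimmune, plus 4×3/2 = 6 both non-autoimmune, giving 27. The other 7×4 = 28 are truly mixed.
- Step 3: 3×2/2 = 3, all both non-autoimmune. No pair is both autoimmune, because the two autoimmune codes share one statement.

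**Pairs that agree at Subgroup 2.** Four statements map to Other autoimmune ILD in each of Steps 1 and 2, so 4×3/2 = 6 in each. Step 3 has none.

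**Pairs giving Multiple, as written → with a separate test for each variable:**

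| Step | Subgroup 1 | Subgroup 2 | Subgroup 3 |
|---|---|---|---|
| 1 | 15 → 0 | 15 → 9 | 15 → 15 |
| 2 | 55 → 28 | 55 → 49 | 55 → 55 |
| 3 | 10 → 7 | 10 → 10 | 10 → 10 |

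These count pairs of statements, not patients.

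**Which patients are reached.** Step 1 needs codes from two statements on the index date itself. Step 2 needs two different earliest codes, read here as a tie on the earliest date, and index code J84.1 or J84.9. With index code 8840951 or 8848245 alone, the Step 2 rule does not apply; the first matching autoimmune statement does, and the patient stays in Autoimmune ILD.

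**Illustration only.** No section gives patient numbers or subgroup risks. Suppose a share f of autoimmune patients is moved, with risk p1 against p0 = 30% in the rest. As written, the stratum reads p0. With those patients restored it reads (1−f)·p0 + f·p1.

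- f = 2%, p1 = 40%: 0.98×30% + 0.02×40% = 30.2%.
- f = 20%, p1 = 50%: 0.80×30% + 0.20×50% = 34.0%.

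Over this assumed range the shift is 0.2 to 4.0 percentage points. It would be zero if the risks were equal and would reverse if p1 were below p0.

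**The case against.** The best defence is that the rule is explicit and prespecified. Note (1) chooses an SLE and PM/DM pair as its example of different codes, Multiple is a listed and reported level of all three variables, and nobody is dropped. The rule also has the convenience that the Multiple stratum is the same set of patients in every subgroup analysis. This makes the rule clear, but it does not justify it. No reason is given, and Annex 5 does not hold to it. Overlap syndrome recorded under its single code (8841317) can be grouped as Autoimmune ILD in Step 2, whereas two tied autoimmune codes with index code J84.9 give Multiple. The same tied codes with index code 8848245 alone stay in Autoimmune ILD. The class then depends on how the disease was coded.

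The objection to scope stands. A reader might infer that every patient with two autoimmune diseases leaves Autoimmune ILD, so that the stratum describes single-disease patients only. The text does not support that. A single Step 1 code with a second autoimmune disease in the lookback stays in the class, as does a patient whose second disease was coded later than the first. Step 3 cannot remove anyone on the strength of two autoimmune codes. A reader might also take Subgroup 1 to be the main comparison, but the protocol does not say so.

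It also stands that the size is unknown. If ties are rare, or the moved patients have similar risk, the effect on the curves is small.

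**Conclusion.** The point holds in limited form. Annex 5 removes a Subgroup 1 label on which the codes agree for 15 of 15, 27 of 55 and 3 of 10 statement pairs in Steps 1, 2 and 3. It removes an agreed Subgroup 2 label for 6 of 15, 6 of 55 and 0 of 10. The Autoimmune ILD loss comes from Step 1 (15 pairs) and Step 2 (21 pairs). The Non-autoimmune ILD loss comes from Step 2 (6 pairs) and Step 3 (3 pairs). Subgroup 3 is not at fault.

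The counts rest on the written labels, and the statement of who is reached in Step 2 rests on reading two earliest codes as a tie. The number of patients and the shift in any subgroup estimate cannot be derived from the documents. Patients move between strata and none leaves the study, so the overall cumulative incidence does not change. Because only descriptive subgroup analyses are affected, this is a should-fix.

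**What to change.** In each step, map every qualifying code to its Subgroup 1, 2 and 3 label. Then assign Multiple separately for each variable, only where the labels differ at that level. For example:

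- SSc and Sjogren codes on the index date: Autoimmune ILD, Multiple, Multiple.
- SLE and PM/DM codes on the index date: Autoimmune ILD, Other autoimmune ILD, Multiple.
- iNSIP and unclassifiable codes in Step 3: Non-autoimmune ILD, Multiple, Multiple.

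Leave the IPF exclusion, and the handling of patients with an IPF code plus another code, as they are. In particular, do not add a rule that ignores J84.9 in Step 3 when a more specific code shares the date. A patient reaching Step 3 with an IPF code and J84.9 is now Multiple and kept. Ignoring J84.9 would leave IPF alone, trigger exclusion criterion 1, and so change the study population and the overall estimate.

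The cost is a few lines in Annex 5 and in the program, with no new data. If the sponsor prefers the present rule, the protocol should give the reason, and the report should show how many patients in Subgroup 1 Multiple are autoimmune-only, non-autoimmune-only and mixed.
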